8.8. Maternal body composition

8.8.1. BOD POD

BOD POD measures body composition using air displacement plethysmography (Life Measurement Inc, Concord, CA) as previously described [60, 61]. Subjects will be clothed in a Lycra-style swim cap and tight fitting underwear or shorts. Body weight will be measured to the nearest 1g. Following standard calibration procedures, body volume of the subject will be measured in the BOD POD and correction made for thoracic gas volume (TGV) which is estimated using the BOD POD breathing circuit system [60]. The final TGV and the average of two body volume measurements that are within 0.2% will be used to calculate body density [60]. In terms of accuracy, the BOD POD has a 2% error relative to hydrostatic weighing and a CV of 2% [61].

8.8.2. Skinfold Thickness

Skinfold thickness will be measured at 6 sites (triceps, biceps, subscapular, iliac crest, mid-calf and mid-thigh) using skinfold calipers.

8.8.3. MRI

Magnetic resonance imaging (MRI) will be performed using a 3.0 T scanner (General Electric, Discovery MR750w, Milwaukee, WI). Subjects will be placed supine on the scanner table with the arms above the head and legs propped up. Subject positioning will be taught and reviewed by a Maternal Fetal Medicine physician to ensure mother and fetal safety. A SPGRE weighted localizer and T1 8 point ME-FSPGRE images will be acquired through the anatomy from the tips of the fingers through the pubic symphysis (waist). The subject will then be repositioned on the table with the head propped up and the pubic symphysis (waist) and legs positioned flat on the table. A SPGRE weighted localizer and T1 8 point ME-FSPGRE images will be acquired from the pubic symphysis (waist) to the bottom of the feet. A total of approximately ~800-1100 T1 8 point ME-FSPGRE images will be acquired on each subject. A frequency of 256, phase of 256, and a field of view of 50 cm will be utilized for the scan. The slice thickness will be 10mm with 10mm interslice gaps. Scan time will be approximately 20-30 minutes with the total mean acquisition time, including positioning of the subject, approximately 30 minutes. Scans will be saved onto CD or DVD and sent to imaging department for analysis, but can also be sent to a third party for analysis. Scans will be performed per Pennington Biomedical SOP 1109. Any abnormal findings identified during scan acquisition or analysis will be documented and reported per this SOP and the incidental findings plan agreed upon by the collaboration of the Principal Investigator, [name], Co-Investigator, [name], and the Pennington Biomedical Imaging Director. These data will also have an additional layer of oversight as [name]. [name] will review each scan within 14 days of acquisition. [name]. [name] is a Co-Investigator of this study and the Director of the Maternal Fetal Medicine Department at Woman's Hospital and as such will follow his standard procedure for identification of an abnormal finding including fetal anomaly which is his area of expertise. This includes, but is not limited to, contacting the participant to discuss the finding, contacting the participant's physician and/or contacting the participant's obstetrician.

Scans will not be performed during the participant's first trimester (12,6 GA or earlier). Gestational age will be determined based on the gestational age determination algorithm below. The MRI will not be performed until the youngest gestational age determination (either algorithm or ultrasound report from participant's obstetrician) is 13,0 or later.

Gestational Age Determination:

Gestational age is determined as follows, and is denoted "project gestational age". The "project EDC", which is based on the project gestational age, cannot be revised once a determination has been made.

Spontaneous Pregnancies

The following algorithm is based upon a comparison of the last menstrual period (LMP) and gestational age as assessed by the earliest dating ultrasound. The algorithm is also applicable to pregnancies where ovulation induction or artificial insemination was used. If a participant has not received a dating ultrasound by the time she has been determined to meet other eligibility requirements, one must be

conducted before randomization can take place (which will also be used to rule out known fetal anomalies). Abnormal findings found on pre-randomization ultrasounds which are performed outside clinical care for the study should be reported to the participant's physician.

Qualifications of the earliest dating ultrasound:

- The ultrasound must have been conducted at 6 weeks or later. This means that if the ultrasound was done early in the first trimester, the crown rump length measurement (CRL) must be at least 4.0 mm.*
- Gestational age cannot be determined by gestational sac measurement.*
- There must be a report or an image showing the biometric parameter(s). A copy of the ultrasound report or image used for gestational age consideration must be kept in the participant's research folder.*
- Information from a participant's chart (such as a doctor's note) without an official report is not acceptable for gestational age determination.*
- The gestational age estimate must be expressed in weeks and days.*

The dating algorithm is as follows:

- The first day of the LMP is determined, and a judgment made as to whether or not the patient has a "sure" LMP date.*
- If the LMP date is unsure, the ultrasound measurements obtained at the patient's first dating ultrasound examination are used to determine the project gestational age, by the standard method of ultrasound gestational age determination at that institution. Ultrasound reports often have more than one gestational age estimate. Choose the gestational age estimate based on the biometric parameter(s) (such as CRL) not the estimate that includes LMP in the calculation.*
- If the LMP date is sure, project gestational age is determined by a comparison between the gestational age by LMP and by the earliest dating ultrasound. Choose the ultrasound gestational age estimate that is based on the biometric parameter(s) (such as CRL) not the estimate that includes LMP in the calculation.*
- If the earliest dating ultrasound confirms the gestational age by LMP within ± 7 days, the LMP-derived gestational age is used to determine the project gestational age.*
- If the ultrasound determined gestational age does not confirm the LMP generated gestational age within ± 7 days, the ultrasound estimate is used to determine the project gestational age.*

In-Vitro Fertilization

The only exception to the algorithm above is the case where the patient has undergone in vitro fertilization (IVF) to achieve pregnancy. If in-vitro fertilization is used (standard IVF, IVF with donor egg/sperm, or IVF with ICSI) and

- the embryo is transferred at three days of age, the project EDC is 263 days after the date of transfer;*
- the embryo is transferred at five days of age, the project EDC is 261 days after the date of transfer;*
- the embryo is transferred at six days of age, the project EDC is 260 days after the date of transfer.*

8.9. Fetal size

Fetal size [62], fetal adiposity [63, 64], and placental metrics will be measured using two dimensional (2-D) and three-dimensional (3-D) ultrasound. Fetal size will be measured early (13-16), mid (24-27 weeks GA) and late (35-37 weeks GA) pregnancy from 2-D conventional biometry which includes measurements of biparietal diameter (BPD), head circumference (HC), transverse diameter and circumference of the abdomen (AC) and femur length (FL) and 2) 3-D volumetry of the fetal thigh, upper arm and abdomen [62]. Fetal adiposity will be obtained from measurements of anterior and lateral abdominal subcutaneous fat thickness, mid-humeral and mid-thigh lean mass, mid-humeral and mid-thigh subcutaneous fat thickness [63, 64]. At least three measurements will be taken and the mean value used in the analysis. During measurements, images of the hands, feet, face, etc. of the fetus may be captured and, upon participant request, may be provided to the participant after review by [name]. [name].

Analysis: All scans from all subjects will be read by the same analyst under the direction of [name]. [name].

8.10. Clinical chemistry and biospecimens

For study use: 30mL of blood (at 5 timepoints, 150mL total over 18 months) will be collected to measure the following: glucose, insulin, thyroxine (T4), tri-iodothyronine (T3), thyroid stimulating hormone (TSH), leptin, total ghrelin, peptide YY, and cholecystokinin.

For future use: 20mL of blood (5 timepoints, 100mL total over 18 months) will be collected if the subject provides permission for samples to be stored for future use. 5mL of urine (5 timepoints, 25mL over 18 months) will be collected if the subject provides permission for samples to be stored for future use. Blood archives will be stored for running the following assays: FGF-21, lipids, ADP, HMWADP, FFA, hsCRP, 25 OH VitD, 1,25 dihydroxy VitD, 4-plex cytokines (IL-1, IL-6, IL-8, TNFa), and DHA/EPA. Placental biospecimens and cord blood will be collected if the subject provides permission for samples to be stored for future use.

8.11. Classification of gestational weight gain

Gestational weight gain will be defined, as recommended by the IOM, as the last measured weight during pregnancy minus the self-reported pre-pregnancy weight [10]. Self-reported pre-pregnancy weight will be validated against chart extracted weights recorded within 6 months of the current pregnancy. If the self-report and the chart extract weight differ too greatly, adjustment of pre-pregnancy weight used will be at the discretion of the principal investigator. The 2009 IOM guidelines for weight gain during pregnancy^[10], will be used to categorize subjects on the basis of gestational weight gain. Subjects with gestational weight gain above the 2009 IOM guidelines (at the time of delivery) will be defined as '*High Gainers*'. Subjects with gestational weight gain within the 2009 IOM guidelines (at the time of delivery) will be defined as '*Normal Gainers*'. Subjects with gestational weight gain below the 2009 IOM guidelines (at the time of delivery) will be defined as '*Low Gainers*' and excluded from the primary analysis.

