2. BACKGROUND AND SIGNIFICANCE

2.1. Definition and prevalence

Currently in the United States, 31.9% of reproductive age women (20-39 years) are estimated to be obese [1] and 8% severely obese [2]. Obesity at conception as well as excess gestational weight gain leads to adverse health outcomes for the mother [3-6] and more alarming, the infant [6-9] that are sustained for decades later.

In an attempt to counteract these trends, the Institute of Medicine (IOM) performed a detailed review of observational data in pregnant women and infants, and defined, within each BMI classification, boundaries for appropriate weight gain during pregnancy [10]. According to the IOM, gestational weight gain in obese women should be limited to 5-9 kg [10]. To be compliant with the gestational weight gain guidelines, the IOM suggests pregnant women receive dietary advice and physical activity counseling throughout pregnancy. Despite these recommendations, recent data in 227,149 obese pregnant women indicate that more than 55% of obese women in the U.S. exceed the IOM guidelines for gestational weight gain [11]. Furthermore, to date, lifestyle interventions specifically designed to attenuate weight gain in obese pregnant women have failed [12-17]. In order to improve weight management in obese pregnant women, there is a critical need to understand the determinants of gestational weight gain. In support of this contention, the IOM recognized that, "there remains a lack of information to relate dietary intake or physical activity to gestational weight gain even though they are primary determinants of weight gain in non-pregnant individuals" [10].

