3. RESEARCH DESIGN

This is a single arm, prospective study. In this study, we will enroll up to 75 obese, pregnant women to complete at least 60. This study will be performed at Pennington Biomedical Research Center in Baton Rouge, Louisiana. Study outcomes will be assessed at three time points during pregnancy; namely, gestational weeks 13-16 (early), 24-27 (mid), and 35-37 (late); and at two time points postpartum; namely, postpartum weeks 22-25 and 48-56 (postpartum testing). Infants born to the mothers enrolled in the MomEE study will complete 1 study visit before 10 days of life to measure anthropometrics, body composition measurements, and questionnaires.

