10.2. Data analysis plan

Analyses will be performed in SAS version 9.3 (SAS Institute, Cary, NC). Statistical significance will be set at $p \leq 0.05$.

Aim 1: Mixed models will be used to analyze differences between 'High Gainers' and 'Normal Gainers' with respect to energy intake during pregnancy estimated with the energy balance method. Adjustments for covariates, such as maternal age, fetal size and parity will be made if appropriate. Least square means will be compared with the mixed models contrasts. Energy intake from the energy balance model will be analyzed analogously in the context of repeated measurements. We expect that energy intake by the two methods will all be significantly higher in 'High Gainers' versus 'Normal Gainers'. In addition, the two methods for measuring energy intake will be cross validated with each other and compared with Bland-Altman analysis. Regression analyses will be used to assess the relationship between energy intake during pregnancy and postpartum weight loss after 1 year. We predict that lower energy intake during pregnancy is associated with better postpartum weight loss results after 1 year.

Aim 2: Analysis of covariance will be used to assess significance of differential changes ('High Gainers' versus 'Normal Gainers') in absolute energy expenditure. Differential changes in energy expenditure after adjustment for changes in maternal and fetal size will be tested analogously. For secondary hypotheses, change in energy expenditure attributable to accelerometer-measured physical activity (steps per min) will be analyzed to investigate its role in differential energy balance in 'High Gainers' versus 'Normal Gainers'.

Analyses of exploratory aims: The change in determinants of energy intake and energy expenditure in blood and urine from early to late pregnancy and 12 months postpartum will be analyzed by repeated measures with IOM classification and time interactions. Adjustments for covariates, such as maternal age, fetal size, parity and early pregnancy values will be made if appropriate. To control for type I error, statistical significance for all multiple comparisons will be adjusted using the Tukey-Kramer method.

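### Pre-pregnancy weight, which sets the High/Normal/Low label, may be adjusted at the principal investigator's discretion, with no threshold, replacement rule, timing or masking stated

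*Combined protocol and SAP*

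**What the plan says.** Section 8.11 defines gestational weight gain as "the last measured weight during pregnancy minus the self-reported pre-pregnancy weight". Self-report is compared with chart weights from within six months of the pregnancy. The rule for disagreement is: "If the self-report and the chart extract weight differ too greatly", then "adjustment of pre-pregnancy weight used will be at the discretion of the principal investigator".

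The IOM guidelines "will be used to categorize subjects on the basis of gestational weight gain", judged at the time of delivery. Section 2.1 gives the range for this population: "gestational weight gain in obese women should be limited to 5-9 kg". Gain above it makes a woman a High Gainer and gain within it a Normal Gainer. Low Gainers, below it, are "excluded from the primary analysis".

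Section 10.2 then sets the Aim 1 analysis: "Mixed models will be used to analyze differences between 'High Gainers' and 'Normal Gainers' with respect to energy intake during pregnancy". Aim 2 compares the same two groups on energy expenditure. On design, Section 3 says: "This is a single arm, prospective study". No masking of anyone to outcome data is described.

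**The concern.** High versus Normal is not randomised. It is derived from two weights, and one of them can be changed by judgement. The plan does not say how large a disagreement triggers the judgement, which value then replaces self-report, when the decision is taken, or whether the person deciding may have seen the energy results. Nor does it ask for a log of changes or a sensitivity analysis.

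Two things are at stake. First, the hypothesis is directional (High Gainers eat more), so labels chosen with knowledge of intake would favor it. Second, even an impartial but inconsistent choice mislabels women and weakens the contrast. Because Low Gainers are dropped, the same judgement can also decide who is analysed.

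**Working it through.** **Route from the rule to the analysis.** Gain = last measured weight − pre-pregnancy weight, so each kilogram added to pre-pregnancy weight lowers gain by one kilogram. The cuts are 5 and 9 kg. The Normal band is 9 − 5 = 4 kg wide with its midpoint at 7 kg, so no Normal Gainer is more than 2 kg from a cut.

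**What is not touched.** In Section 8.13, energy intake is total daily energy expenditure plus the change in energy stores between weeks 13-16 and 35-37. Pre-pregnancy weight does not enter. The discretion can therefore alter labels and inclusion, not this outcome's values.

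**Timing.** Doubly labeled water, chamber and MRI measurements are made at weeks 35-37 (Table 1). Labels rest on gain at delivery, so the outcome data can exist before a label is final.

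**How many adjusted women change category.** The documents give no distribution of gain. Assumption: normal, mean 8-12 kg, SD 4-6 kg. If gain falls by x kg, for x up to 4, the women who cross a cut are those with gain in (5, 5+x) or (9, 9+x). If gain rises by x, they are those in (5−x, 5) or (9−x, 9).

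Example with mean 8, SD 4 and pre-pregnancy weight raised by 2 kg: [Φ((7−8)/4) − Φ((5−8)/4)] + [Φ((11−8)/4) − Φ((9−8)/4)] = (0.4013 − 0.2266) + (0.7734 − 0.5987) ≈ 0.349.

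| Change in pre-pregnancy weight | Lowered | Raised | Either direction |
|---|---|---|---|
| 1 kg | 9-17% | 10-17% | 9-17% |
| 2 kg | 15-32% | 21-35% | 15-35% |
| 3 kg | 19-45% | 32-52% | 19-52% |

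These are shares of the adjusted women only. Five women adjusted by 2 kg would give 5 × 0.15 to 5 × 0.35, or about 0.8 to 1.8 relabelled women.

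The assumed distributions imply 19-37% Normal and 40-77% High, more High Gainers than Section 10.1 plans for. That section's figures (10% Low; High to Normal 1:2, hence 30% and 60%) would, under normality, need mean 7.8 kg and SD 2.2 kg. The shares are then larger: 23-24%, 43-48% and 59-70%.

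**Effect on the contrast, as an illustration.** The base is the last row of Table 4: 17 and 34 women, SD 700 kcal/d, difference 590 kcal/d, power .80. Check: SE = 700 × √(1/17 + 1/34) = 207.9; 590/207.9 = 2.84; Φ(2.84 − 1.96) = 0.81. The noncentral t gives 0.794. The row reproduces.

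A simulation (6,000 runs per setting, two-sample t-test, two-sided 0.05) then left the label of m of the 51 women open. The values of m are assumptions.

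| m | Type I error if label follows intake | Spurious difference, kcal/d | Power at 590 kcal/d if label is random |
|---|---|---|---|
| 0 | 5% | 0 | 79% |
| 3 | 6% | 68 | 73% |
| 5 | 8% | 119 | 69% |
| 8 | 15% | 190 | 62% |
| 10 | 20% | 233 | 57% |

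The type I error and spurious-difference columns are a worst case: every open label is High if intake is above the median, and there is no true difference. With random labels, type I error stays near 5%. Here m counts women whose label the discretion actually decides, which is fewer than the women adjusted.

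**The case against.** The discretion is an exception. Self-report is the default, and the clause applies only after a disagreement with the chart. That is correct, but a trigger without a number does not limit how often the exception is used.

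A reader might infer that the judgement is unblinded. The documents do not establish this. They are silent on what the investigator will have seen, and Section 9.4, which gives investigators database access, is a confidentiality clause about identifiable records, not computed intake. Self-report is collected at screening (Section 8.7), so where a chart weight is also to hand the decision could precede every outcome measurement. What stands is that the plan does not require this.

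A reader might also infer that any bias could never be checked afterwards. That is not supported either. Self-report is recorded at screening, chart weights are extracted, and nothing says that either is overwritten, so labels can be recomputed from each source.

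Finally, the 6-20% type I error range needs deliberate labelling by intake, which nothing in the documents suggests. It marks an outer limit and is not a forecast.

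**Conclusion.** The point holds in a bounded form. Section 8.11 leaves the input to the primary grouping variable open to discretion, and no other section limits it. The plan does not prevent outcome knowledge from influencing labels, but it does not say that this will happen. Only labels and inclusion are exposed for the energy balance outcome.

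The size cannot be fixed, because the number of women adjusted is unknown. Among those adjusted, about 9-17%, 15-35% or 19-52% would change category for 1, 2 or 3 kg, assuming normal gain with mean 8-12 kg and SD 4-6 kg. The effect on the contrast depends further on how many labels are truly open. With few it is small, and arbitrary labelling costs power even when nobody looks at outcomes. The rule should be changed, since doing so is cheap and uses weights already collected.

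**What to change.** Replace the discretion in Section 8.11 with three elements.

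1. A discrepancy threshold in kilograms, chosen and justified by the sponsor, and a fixed replacement rule. One option: above the threshold, use the chart weight nearest conception within the six-month window; otherwise, or with no such chart weight, use self-report. The threshold needs a reason, because a tolerated disagreement of 2 kg could itself separate categories for 15-35% of the women concerned.
2. Application of the rule, with a log of each change, by staff without access to doubly labeled water, MRI or chamber results, before energy intake is computed.
3. Two sensitivity analyses of the primary contrast in Section 10.2: all labels from self-report, and labels from chart weight in the women who have one.

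The cost is one paragraph and two extra runs, with no new data. The chart-only run covers only women with a chart weight in the window, so it will be smaller and should be reported with its count.

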8.12. Measurement of maternal body composition

MRI will be used to quantify total adipose tissue mass, skeletal muscle mass and non-adipose tissue mass volumes in the mother during pregnancy and at 12 months postpartum. To investigate the contribution of the fetus to energy metabolism, we will estimate maternal fat mass and fat-free mass both with and without the inclusion of fetal size.

Total adipose tissue volumes (called fat mass, FM) will be measured by MRI and converted to kilograms as previously described [65-67]. Non-adipose tissue volume (called fat-free mass, FFM) will be calculated as;

$$FFM_{TOTAL} \text{ (kg)} = \text{Total maternal mass including fetus (kg)} - \text{fat mass (kg)}$$

$$FFM_{Maternal} \text{ (kg)} = [\text{maternal mass} - \text{fetal size* (kg)}] - \text{fat mass (kg)}$$

*The mass of the fetus will be measured with 3-D ultrasound as described above.

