complete while in the chamber. Lights will be turned out at about 10:30 PM. Subjects will be asked to collect all urine overnight. Subjects will be woken in the morning and asked to void. Next, subjects will remain awake, and resting metabolic rate (RMR) will be measured for approximately 30 minutes. Subjects will exit the chamber and their body weight and vital signs will be measured. Accelerometers may be removed and downloaded. A fasting blood draw will be collected and if the subjects have given permission, additional blood will be collected and stored for future use. Subjects will have neck circumference and body composition by BOD POD, and skinfolds measured. Then, subjects will be offered breakfast and RFPM training will be performed. Next, subjects may have a whole body MRI scan to measure total adipose tissue mass and skeletal muscle mass and a 3-D ultrasound to measure the size of her fetus or they may choose to do this at an additional visit if desired. Actigraph will be placed back on the subject's wrist and will be returned with the timed urine samples for the doubly labeled water study collected 6 and 7 days later.

The study visit as described above will be performed at the early pregnancy, late pregnancy and 12 months postpartum (excluding the ultrasound) time points. Additionally at 12 months postpartum, an oral glucose tolerance test will be conducted. At the mid pregnancy time point, weight, vital signs, body composition measurements (MRI, skinfold thickness and BOD POD), neck circumference, 3D ultrasound, blood collection, and blood/urine archive (if consented) will be collected or performed. An abbreviated visit at 6 months postpartum will be conducted to collect weight, vital signs, blood, neck circumference, body composition by BOD POD and skinfold thickness, and blood/urine archive (if consented). Questionnaires will be administered at each visit. Participants will receive handouts with some of their study results. Prenatal vitamins will be provided to participants during pregnancy and compliance assessed at subsequent visits. Participants will be provided a scale to take home to continuously weigh themselves throughout the study. Data from prenatal, delivery, and neonatal records will also be obtained from the participants' respective physicians.

Table 1.	Screening Visit	Early Pregnancy	Mid Pregnancy	Late Pregnancy	Delivery	6 months after delivery	12 months after delivery

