8.13. Measurement of energy intake by energy balance method

Energy intake will be calculated from total daily energy expenditure measured by DLW and the changes in body energy stores (Δ ES) using the following equations: Energy intake (kcal/d) = Total daily energy expenditure + Δ Energy Stores where, Δ energy stores, was calculated using the actual change in fat mass (kg) and total fat-free mass (kg) between the late pregnancy (weeks 35 to 37) and early pregnancy testing (weeks 13 to 16) multiplied by the energy coefficients for fat mass and total fat-free mass. The energy density of fat mass has been well-established as approximately 9300 kcal/kg and has been validated in pregnant women [68]. Energy density of fat-free mass differs during pregnancy [69] and we will use 771 kcal/kg as previously determined for pregnant women [70]. Therefore: Δ Energy stores (kcal/d) = (9300 x Δ fat mass, kg/d) + (771 x Δ total fat-free mass, g/d).

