10. DATA MANAGEMENT

10.1. Statistical power and sample size

The primary outcome is energy intake during pregnancy. We were able to apply the energy-balance model to

Table 4. Minimum sample size for power at .80 and .90, ratio between groups 1:2

Standard Deviation kcal/d	Mean Difference kcal/d	Power (β)	Group 1 N	Group 2 N
700	541	.90	27	54
700	468	.80	27	54
700	600	.90	22	44
700	520	.80	22	44
700	688	.90	17	34
700	590	.80	17	34

estimate energy intake in previously reported data on energy requirements during pregnancy [82]. The standard deviation of energy intake in the third trimester was conservatively estimated to be 700 kcal/d using Butte’s data on total energy expenditure and energy deposition of fat mass and fat-free mass.

We hypothesize that women who will exceed 2009 IOM recommendations for weight gain during pregnancy, the ‘High Gainers’, will have a larger energy intake than those who will keep their weight gain within IOM guidelines, the ‘Normal Gainers’. Because of the intervention, we predict to have a decrease in the incidence of ‘High Gainers’ from 66% to a rate below 50%. Therefore we predict that the ratio “High Gainers” to “Normal Gainers” will likely be 1:2. Our power/sample size analysis (Table 2) assumed: 1) power ≥ 0.90 , 2) alpha = 0.05, 3) the null hypothesis will be tested against a two-directional alternative, 4) the common standard deviation for energy intake is 700 kcal/d and 5) conservative estimates that the ratio between the two groups, ‘High Gainers’ to ‘Normal Gainers’ is 1:2.

As shown in Table 2, with subject assignment to the 2009 IOM guidelines being 1:2, we require a minimum of 51 subjects, to detect a between group difference of 590 kcal/d with 90% power or 520 kcal/d with 80% power. To allow for early deliveries, the inability to perform MRI in some subjects late pregnancy, due to limitations with the field of view, and that 10% of subjects will gain less weight than recommended; we aim to complete at least 60 subjects.

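### MRI adipose tissue is labelled fat mass and valued at the energy density of fat with no stated lipid fraction, which as written overstates stored energy and may modestly inflate the intake contrast

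*Combined protocol and SAP*

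**What the plan says.** Section 7 describes a "whole body MRI scan to measure total adipose tissue mass and skeletal muscle mass". Section 8.12 turns that measurement into the two compartments used later. For the first it says: "Total adipose tissue volumes (called fat mass, FM) will be measured by MRI and converted to kilograms as previously described", citing references 65 to 67. For the second it says: "Non-adipose tissue volume (called fat-free mass, FFM) will be calculated as" body mass minus that fat mass, in one version with the fetus included and in another with fetal mass taken off.

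Section 8.13 computes energy intake as doubly labeled water expenditure plus the daily change in energy stores between the early and late pregnancy visits. On the first coefficient it says: "The energy density of fat mass has been well-established as approximately 9300 kcal/kg". On the second it says: "we will use 771 kcal/kg as previously determined for pregnant women". The first multiplies the change in fat mass, the second the change in total fat-free mass.

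Neither section states a lipid fraction for adipose tissue or a separate coefficient for adipose tissue. Energy intake is the first-listed primary outcome (3.1), and Hypothesis 1 expects it to be larger in High Gainers (2.2).

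**The concern.** The quantity measured and the coefficient applied to it do not match as written. If fat mass is whole adipose tissue and fat-free mass is what lies outside adipose tissue, then any water and protein inside adipose tissue sits in fat mass and is valued at 9300 kcal/kg. On the plan's own two-compartment scheme that part belongs with the 771 kcal/kg compartment.

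The error is not random noise. It grows with adipose gain, and the groups are formed by gestational weight gain (8.11). If High Gainers gain more adipose tissue than Normal Gainers, the error raises their computed intake by more and moves the primary contrast in the hypothesised direction. It also affects the absolute intake figures. The planned Bland-Altman comparison of the two intake methods (10.2) would show it as disagreement between methods.

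The point concerns the energy balance method. The documents do not show the mathematical model using MRI fat mass.

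**Working it through.** **1. The plan's own design figure.** Section 10.1 states that "the null hypothesis will be tested against a two-directional alternative", with alpha 0.05, and that "the common standard deviation for energy intake is 700 kcal/d". For 17 + 34 women, Table 4 gives 590 kcal/d at power 0.80 and 688 kcal/d at 0.90. The standard error of the contrast is 700 × √(1/17 + 1/34) = 208 kcal/d. Power from the t distribution is 0.79 at 590 and 0.90 at 688, so the table reproduces. The text beside it gives 590 at 90% and 520 at 80% for the same 51 women. That is a separate inconsistency. Here I use 520 to 688 kcal/d as the range of design differences.

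**2. Inputs from the documents.**
- Coefficients (8.13): 9300 and 771 kcal/kg, difference 8529.
- Interval between visits: (35 − 16) × 7 = 133 days at the shortest, (37 − 13) × 7 = 168 at the longest, (36 − 14.5) × 7 = 150.5 at the midpoints.
- I take the change in fat-free mass in kg/d. The printed formula has g/d, which does not fit a coefficient per kg and is also a separate matter.

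**3. Inputs the documents do not give (assumptions).**
- Lipid fraction f of the tissue gained: 0.80, range 0.70 to 0.90.
- Difference D in adipose gain, High minus Normal Gainers: 4 kg, range 2 to 6 kg.

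**4. Overstatement per kg of adipose gain.** Stated value 9300; matched value 9300f + 771(1 − f); excess (1 − f) × 8529.

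| f | Matched coefficient (kcal/kg) | Excess (kcal/kg) | Stated over matched |
|---|---|---|---|
| 0.70 | 6741 | 2559 | 38% too high |
| 0.80 | 7594 | 1706 | 22% too high |
| 0.90 | 8447 | 853 | 10% too high |
| 1.00 | 9300 | 0 | none |

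**5. Effect on the contrast.** Inflation = D × (1 − f) × 8529 / days. At 150.5 days, in kcal/d:

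| f | D = 2 kg | D = 4 kg | D = 6 kg |
|---|---|---|---|
| 0.70 | 34 | 68 | 102 |
| 0.80 | 23 | 45 | 68 |
| 0.90 | 11 | 23 | 34 |
| 1.00 | 0 | 0 | 0 |

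Extremes over the visit windows: 2 × 853 / 168 = 10 and 6 × 2559 / 133 = 115 kcal/d.

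**6. Scale.** The central 45 kcal/d is 9% of 520, 8% of 590 and 7% of 688. It is 5% of the preliminary contrast in section 2.1 (3503 − 2617 = 886 kcal/d), and 45/208 = 0.22 of a standard error. The upper end is 115/208 = 0.55 of a standard error. If a contrast of 590 contained 45 kcal/d of this error, removing it with the SD held at 700 would take power at 17 + 34 from 0.79 to 0.73. The SD would shrink as well if the stores term were rescaled, so the net effect on power could go either way.

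**7. A term in the other direction.** Total fat-free mass includes the fetus, so fetal fat is valued at 771 kcal/kg unless that coefficient already allows for it. If fetal lipid gain were 0.2 to 0.4 kg (assumption), stores would be understated by 0.2 × 8529 = 1706 to 0.4 × 8529 = 3412 kcal, or 11 to 23 kcal/d over 150.5 days. At f = 0.80 this cancels the overstatement on 1 to 2 kg of maternal adipose gain. It bears on the level of intake more than on the group contrast.

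**8. What is not affected.** The adjusted expenditure in 8.14 regresses on both fat mass and fat-free mass. With one common f, replacing fat mass by f times itself and moving the remainder to fat-free mass only re-expresses the same two predictors, so the predicted values do not change.

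**The case against.** The strongest reply is that the step which matters lies in sources not available here. A lipid fraction or a choice of density could enter when the volume is converted to kilograms, and 8.12 leaves that to references 65 to 67. The wording of 8.12 is also loose: it calls fat-free mass a volume and then computes it in kilograms. A reader might infer that stores are certainly overstated and the contrast certainly inflated. The documents do not establish that. It depends on the conversion, on the composition of the tissue gained rather than of the whole depot, and on a group difference in adipose gain that is not reported.

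A reader might also infer that the error could produce the Hypothesis 1 result. The figures do not support this: even the upper end of the assumed range is well under one standard error. Nor do the documents show a net overstatement of absolute intake, because the fetal term runs the other way. The second intake method and the BOD POD measurements give partial cross-checks.

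These points limit the size and certainty of the concern. They do not remove the mismatch. The references are cited only for conversion to kilograms. If they do take out the non-lipid part, then body mass minus fat mass is no longer non-adipose tissue, and the labels in 8.12 need correcting. The text needs a change in either case. Bland-Altman agreement could reveal a difference between methods but would not identify its cause.

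**Conclusion.** The point holds in conditional form. Read as written, 8.12 and 8.13 apply the energy density of fat to whole adipose tissue and overstate stored energy by (1 − f) × 8529 kcal per kg of adipose gain. The exception is a cited conversion that already corrects for this, and then the labels are wrong. The contrast is tilted towards Hypothesis 1 only if High Gainers gain more adipose tissue.

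The size rests on assumed values for f and for the group difference: about 45 kcal/d in the central case, 10 to 115 kcal/d over the range examined, and zero if the added tissue is pure lipid. This is a modest bias in a primary outcome that would not create the contrast alone. It is worth correcting because its expected direction favours the hypothesis and the correction is simple.

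**What to change.** In 8.12 and 8.13, state how adipose volume becomes kilograms, and convert adipose tissue mass to lipid with a stated and sourced lipid fraction before applying 9300 kcal/kg. Move the non-lipid part to fat-free mass at 771 kcal/kg; this follows automatically if fat-free mass stays defined as body mass minus the corrected fat mass. If the cited conversion already does this, say so and correct the two labels instead.

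Report the High versus Normal Gainer intake contrast at two or three lipid fractions fixed in advance. Repeat it with BOD POD fat mass, which Table 1 schedules at the same early and late visits. BOD POD has measurement error of its own (8.8.1 gives 2% against hydrostatic weighing), so it serves as a sensitivity analysis and not as a reference standard.

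The cost is one constant in the derivation program and one sensitivity table, with no new data. The estimated intake difference may become slightly smaller.
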